6. TRIAL DESIGN

6.1. Study Endpoints

Primary endpoints, correlating to the primary objective of the study, will include determining the nature, frequency, and severity of AEs and/or SAEs associated with TDS-EP-based administration of HTNV, PUUV and HTNV/PUUV DNA vaccines.

- The occurrence of solicited local and systemic AEs occurring from the time of each injection through 14 days following the procedure
- The occurrence of vaccine-related unsolicited AEs from the time of the first injection through 28 days following each injection
- The occurrence of SAEs from the time of the first injection through the final study visit (approximately 6 months post-last vaccination)
- The occurrence of clinical safety laboratory AEs through 14 days following each study vaccination

Secondary endpoints, correlating to the secondary objectives of the study will be to determine the proportion of seropositive subjects ($\text{PsVNA50} \geq 1:20$) and the final overall rate of seroconversion over all scheduled time points to study completion for each study group. GMT will be calculated using PsVNA50 .

- Determination of the proportion of seropositive subjects (defined as $\text{PsVNA50} \geq 1:20$) at each scheduled time point (eg, Days 0, 28, 56, 84 and 140)
- Determination of the final overall rate of seroconversion over all scheduled time points to study completion for each study group. Seroconversion is defined as a post-vaccination HTNV- or PUUV-specific titer of $\geq 1:40$, or a minimum four-fold rise compared to baseline titer, and all study volunteers will begin the study with a baseline titer < 20 (ie, seronegative).
- Determination of GMT of the PsVNA50 for HTNV- and PUUV-specific neutralizing antibodies at each scheduled time point for each study group and over all time points for each study group.

Exploratory endpoints, evaluated as part of the immunogenicity objectives, including calculation of PsVNA80 titers for HTNV and PUUV may be calculated from the collected data for informational purposes, and neutralization assays using other hantavirus PsV (eg, Seoul virus, Dobrava virus) may also be performed to evaluate levels of cross-neutralizing antibodies.

- Determination of GMT of neutralizing of the PsVNA80 for HTNV- and PUUV-specific neutralizing antibodies at each scheduled time point for which blood samples are taken for each study group and over all time points for each study group

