^c Safety lab results will not be reviewed prior to product administration, and inclusion/exclusion criteria will be applied, with the exception of exclusion criteria 9, which will not be applied for vaccinations 2 and 3 because it is for screening prior to enrollment.

^d Physical examination will be completed at screening visit 1, and includes examination of general appearance, skin, neck (including thyroid), eyes, nose, throat, lungs, heart, abdomen, lymph nodes, extremities, and a basic neurological assessment; directed physical exams will be completed at all other visits. A directed physical exam is defined as a focus, complaint-driven physical examination. In the absence of a complaint, a physical exam will not be performed.

^e Reactogenicity assessments will include subject completion of a memory aid each day for 14 days after a vaccination visit.

^f Vital sign measurements include oral temperature, heart rate, respiratory rate, and systolic and diastolic blood pressure.

^g Complete blood count (CBC [WBC, Hb, platelets] with differential), glucose, creatinine, AST, ALT, total bilirubin. Lab abnormalities will be followed up on an ad hoc basis as per the study investigators. At Screen 1, a collection of 2.7 mL blood will be used to perform the PT/PTT tests to determine any coagulation abnormalities for exclusion criterion 25.

^h Blood will be drawn prior to study product administration. Safety lab results will not be reviewed prior to product administration.

ⁱ Approximately 10 mL of blood will be collected at Screen 2 to determine subject eligibility.

^j Blood collected for the humoral immune response to vaccination will be approximately 10 mL on Days 0, 28, 56 and 140; any remaining blood will be stored for future use. Approximately 50 mL of blood will be collected on Day 84 for humoral immune response to vaccination and for future use.

For determination of any cardiac abnormalities, an ECG will be performed at Screen 1 and study visit 11.

ⁿ Procedures will be completed only if Screen Visit 2 falls outside of the 56-day screening window prior to vaccination. See Section 8.1.2 for further clarification

^o Scripted telephone contact for collection of Serious Adverse Event information

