6.6. Study Halting Criteria

Further enrollment and study vaccinations will be halted for SMC review/recommendation if any of the following are reported:

- Any subject experiences a study product-related SAE from the time of the study product administration through the subject's last study visit.
- Any subject experiences laryngospasm, bronchospasm, or anaphylaxis within 1 day after administration of study product that is considered related to study product.
- Two or more subjects experience generalized urticaria (defined as occurring at more than 2 body parts) within 3 days after administration of study product that is considered related to study product.

This trial will also be halted for SMC review/recommendation if, within 7 days after administration of any study vaccination, any of the following occurs:

- Two or more subjects experience a Grade 3 unsolicited AE in the same MedDRA system organ class (captured by preferred term) after administration of study product that is considered related to study product and not resolved or improved to lower grade within 2 days.
- Two or more subjects experience the same Grade 3 solicited local adverse event that is considered related to study product and not resolved or improved to lower grade within 2 days.
- Two or more subjects experience the same Grade 3 solicited systemic adverse event that is considered related to study product and not resolved or improved to lower grade within 2 days.
- Two or more subjects experience the same Grade 3 laboratory adverse event that is considered related to study product.

Grading scales for solicited local (application site) and systemic (subjective and quantitative) AEs are included in Section [10.5](#) and [Appendix C](#).

Grading scales for clinical safety laboratory adverse events are included in Section [10.5](#) and [Appendix C](#).

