8.1.3. Vaccination Visits

There will be 3 primary vaccination visits: Day 0, Day 28 ± 4 days, and Day 56 ± 4 days. Subjects will receive up to 3 vaccinations in the outer aspect of the subject's upper arm (deltoid area; alternating arms, beginning with left, if possible), using the TDS-IM V1.0 or TDS-ID EP system during the course of the study. Vaccine composition, vaccine dose and schedules (per group), subject randomization, and the TDS EP system have been discussed earlier in this protocol.

The following procedures will be performed during each vaccination visit:

- Review subject's medical history including concomitant medication use since screening or previous vaccination
- Review eligibility criteria with subjects and safety criteria including AEs, prior to study vaccination to ensure continued eligibility (see Section 7.5)
- Do a directed physical examination if indicated based on the subject's interim medical history (see also [Table 4](#)). Assess injection site prior to study vaccination to establish a baseline.

- Take resting vital sign measurement including oral temperature, heart rate, respiratory rate, and systolic and diastolic blood pressure. Subjects must not eat or drink anything hot or cold, or smoke within 10 minutes prior to taking oral temperature.
- Weigh subject, and if there is a $> 15\%$ change in body weight, measure skinfold thickness at potential injection sites with a caliper
- Perform a buccal swab for human leukocyte antigen (HLA) testing (Day 0 only)
- Collect approximately 22.5 mL of whole venous blood for the determination of:
 - CBC (WBC, Hb, platelets) with differential
 - Glucose, Cr, AST, ALT, total bilirubin
 - HTNV and PUUV-specific antibody as measured by PsVNA, using approximately 10 mL of the total 22.5 mL blood
- Urine sample collection for determination of pregnancy (must be negative prior to administration of the vaccine)
- Injection with study product
- Post-injection observation period/reactogenicity assessment (Subjects will be kept under observation for at least 30 minutes after each inoculation to ensure their safety, and any reactions during this period will be documented. Appropriate medical equipment and emergency medications, including epinephrine [1:1000], will be available on site in the event of an anaphylactic or other immediate allergic reaction.)
 - Give subject ruler and thermometer and explain how to use (Day 0 only)
 - Distribute memory aid and teach them how to complete memory aid

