8.1.4. Follow-Up Visits

There will be 9 follow-up visits: Day $2 + 1$ day, Day 14 ± 2 days, Day 30 ± 1 day, Day 42 ± 2 days, Day 58 ± 1 day, Day 70 ± 2 days, Day 84 ± 4 days and Day 140 ± 7 days and D220 Phone Call ± 14 days

The following procedures will be performed during each follow-up visit (some exceptions):

- Review of subject's medical history (including concomitant medications and AE) since previous visit
- Directed physical examination (injection site) if indicated based on the subject's interim medical history

- Take resting vital sign measurement including oral temperature, heart rate, respiratory rate, and systolic and diastolic blood pressure. Subjects must not eat or drink anything hot or cold, or smoke within 10 minutes prior to taking oral temperature.
- Review and collect memory aids (Days 14, 42, 70)
- Collect approximately 12.5 to 72.5 mL (depending on the scheduled visit day, see [Table 4](#)) of whole venous blood for the determination of:
 - CBC (WBC, Hb, platelets) with differential (Days 14, 42, and 70 only)
 - Glucose, Cr, AST, ALT, total bilirubin, (Days 14, 42, and 70)
- Collect blood for determination of HTNV- and PUUV-specific antibodies as measured by PsVNA assay (Days 84 and 140)
- Collect approximately 50 mL of blood for future research on Day 84 only
- Collect blood sample for determination of pregnancy test (Day 140 only)
- Perform ECG as last assessment of cardiac normality (Day 140 only)

Day 140 will be the final scheduled in-clinic visit for all subjects

Serious Adverse Event Final Telephone Follow Up Visit

There will be a scripted telephone follow up visit conducted at Day 220 ± 14 days.

- Review and collection of serious adverse events occurring since last visit conducted at Day 140.

Early Termination Visits

If a subject leaves the study early (see also Section [7.5](#)), procedures pertaining to Day 140 in the follow-up visit section (Section [8.1.4](#)) will be followed:

- Review of subject's medical history (including concomitant medications and AE) since previous visit
- Directed physical examination (injection site) and resting vital signs check (oral temperature (no recent hot or cold beverages or smoking), heart rate, respiratory rate, and systolic and diastolic blood pressure)
- Review and collection of any remaining memory aids
- HTNV- and PUUV-specific antibodies (PsVNA50 for final visit)
- Serum sample collection for determination of pregnancy test
- Perform ECG

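### The Grade 3 laboratory halting rule is limited to 7 days after a dose, and no scheduled post-dose safety sample falls in that window

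*Protocol*

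**What the plan says.** Protocol 6.6 has two sets of halting criteria. The second opens with "This trial will also be halted for SMC review/recommendation if, within 7 days after administration of any study vaccination, any of the following occurs". Four bullets follow, and the last is the laboratory rule: "Two or more subjects experience the same Grade 3 laboratory adverse event that is considered related to study product". SAP 4.1.1 has the same layout. The Synopsis has the same wording, but numbers the lead-in and the bullets as one list.

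The sampling schedule is set elsewhere in the protocol:

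- **Dosing (8.1.3):** "There will be 3 primary vaccination visits: Day 0, Day 28 ± 4 days, and Day 56 ± 4 days".
- **Follow-up haematology (8.1.4):** "CBC (WBC, Hb, platelets) with differential (Days 14, 42, and 70 only". Chemistry is on the same three days, and SAP 8.8 lists matching visits.
- **Visit windows (8.1.4):** "Day 14 ± 2 days, Day 30 ± 1 day, Day 42 ± 2 days"; Day 70 is also ± 2 days.
- **Dosing-day laboratories (Table 4, footnote h):** "Blood will be drawn prior to study product administration". The same footnote says the results are not reviewed before the injection.
- **Visits within 7 days of a dose (Days 2, 30 and 58):** Table 4 and Appendix D show no safety laboratory and a blood volume of 0 mL.
- **Unscheduled samples (Table 4, footnote g):** "Lab abnormalities will be followed up on an ad hoc basis as per the study investigators".

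The laboratory safety endpoint in Protocol 6.1 has a longer window than the halting rule: "The occurrence of clinical safety laboratory AEs through 14 days following each study vaccination".

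**The concern.** A 7-day limit suits the other three bullets. Solicited and unsolicited clinical events can be seen in that time through the daily memory aid and the Day 2, 30 and 58 visits. A laboratory change without symptoms is seen only when blood is drawn, and none is scheduled then. As written, two subjects with the same related Grade 3 abnormality at Day 14, 42 or 70 would not trigger the rule.

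Safety is the primary objective, and Protocol 6.2 states that doses reach 6 mg, against up to 2 mg in earlier trials of these vaccines. A halt at these draws would still be in time to matter. The Day 14 and Day 42 samples come before the same subject's next dose and, with staged enrolment, before other subjects are dosed at all. The dosing-day laboratories do not fill the gap, because their results are not read before the injection.

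**Working it through.** The plan gives no figure to reproduce here. The check lists the interval from each dose to the next scheduled safety sample.

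**Inputs.** Doses on Day 0, Day 28 ± 4 and Day 56 ± 4 (Protocol 8.1.3). Post-dose samples on Days 14, 42 and 70, each ± 2 (Protocol 8.1.4).

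**Formulas, with windows counted from Day 0.**
Shortest gap = (sample day − sample window) − (dose day + dose window).
Longest gap = (sample day + sample window) − (dose day − dose window).

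| Dose → sample | Shortest gap | Longest gap | Permitted day pairs | Pairs ≤ 7 days | Pairs ≤ 14 days |
|---|---|---|---|---|---|
| Dose 1 → Day 14 | 12 − 0 = 12 | 16 − 0 = 16 | 1 × 5 = 5 | 0 | 3 |
| Dose 2 → Day 42 | 40 − 32 = 8 | 44 − 24 = 20 | 9 × 5 = 45 | 0 | 25 |
| Dose 3 → Day 70 | 68 − 60 = 8 | 72 − 52 = 20 | 9 × 5 = 45 | 0 | 25 |

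If windows are counted from the actual dose, the gap is 14 ± 2, so 12 to 16 days after every dose. On either reading no permitted pair is within 7 days. The pre-dose samples do not help: Day 28 is at least 24 days after dose 1, and Day 56 is at least 52 − 32 = 20 days after dose 2.

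**Time left to act, counted from Day 0.** Day 14 sample to dose 2: 24 − 16 = 8 to 32 − 12 = 20 days. Day 42 sample to dose 3: 52 − 44 = 8 to 60 − 40 = 20 days.

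**Subjects still to be enrolled.** Appendix B gives 36 already enrolled and 2 + 24 + 20 = 46 to come (82 − 36 = 46). That is 46 × 3 = 138 planned doses, each with one post-dose sample, and 0 of those 138 samples fall within 7 days. The last 20 subjects are conditional: Protocol 6.2 allows them only if their enrolment can be completed within 4 months. The unconditional remainder is 2 + 24 = 26 subjects, or 78 doses.

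**Chance that the rule would have mattered.** The documents give no rate of related Grade 3 laboratory events. Let p be the assumed chance that a subject has one given related Grade 3 abnormality at the scheduled draws. With independent subjects:

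P(two or more) = 1 − (1 − p)^n − n·p·(1 − p)^(n − 1).

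For n = 46 and p = 0.01: 1 − 0.6298 − 0.2926 ≈ 0.078.

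| Assumed p | n = 26 | n = 46 |
|---|---|---|
| 0.5% | 0.8% | 2.2% |
| 1% | 2.8% | 7.8% |
| 2% | 9.5% | 23.4% |

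In every cell the chance of an automatic halt from those draws under the current text is zero.

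**The case against.** The strongest reply is that laboratory safety is still protected by other means:

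- A Grade 4 abnormality must be reported as an SAE (Protocol 10.5), so a related one halts the trial at any time.
- The investigator or DMID can call an ad hoc SMC meeting (10.1.4).
- The research monitor can stop the study (10.1.1), as can the parties named in 6.6.2.
- The investigator may stop a subject's dosing for an ongoing Grade 3 event (7.5), and these criteria are reviewed before each vaccination (8.1.3).
- In an open-label, single-site trial under continuous safety review, a second related Grade 3 result would probably be noticed.

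All of this stands, and it limits the finding to the missing automatic halt. Apart from the SAE rule, though, each route depends on someone choosing to act, and a pre-specified halting rule exists so that review does not depend on that.

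Earlier experience also gives no support for the higher assumed rates. In the earlier Phase 1 trial of 31 subjects, none of the eight Grade 3 or 4 events was rated more than unlikely to be related (4.4.2.1.2). Laboratory abnormalities seen with the intramuscular device were generally mild to moderate (4.5.1.2). That is a fair caution about how often the rule would matter; it does not bear on whether the rule can fire.

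The Synopsis numbering might suggest that its laboratory item is free of the 7-day limit. The lead-in wording and the layout of Protocol 6.6 and SAP 4.1.1 do not support that reading.

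**Conclusion.** The concern holds. The earliest scheduled in-window post-dose sample is 8 days after a dose (12 if windows are counted from the dose), so the rule can be met only by an unscheduled or out-of-window sample. The result rests on the stated visit days and windows and on dating an event by sample collection. Dating by report could move Day 28 or Day 56 pre-dose results into the window after the next dose, but that is a strained reading.

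The gap is specific: repeated related Grade 3 laboratory events found at scheduled draws. It covers all 138 planned post-dose samples of the 46 remaining subjects, or 78 if the conditional 20 are not enrolled. The probability of needing the rule depends wholly on assumed rates. Whether this is an essential or merely advisable correction can be argued, but a stated safety rule that no planned sample can trigger is wrong as written.

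**What to change.** In Protocol 6.6, the Synopsis and SAP 4.1.1, move the laboratory bullet out from under the 7-day lead-in and give it its own period: from each vaccination through the scheduled Day 14, 42 or 70 safety laboratory visit, including that visit's window. Leave the 7-day limit on the other three bullets.

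A plain 14-day limit is not enough. With windows counted from Day 0, it captures only 3 of 5 permitted day pairs after dose 1 and 25 of 45 after each of doses 2 and 3. The proposed period can run past the 14-day laboratory endpoint, to 16 days after dose 1 and 20 days after doses 2 and 3. A halting rule need not match the endpoint window, but the text should say that the difference is intended.

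The cost is three text edits and the approvals that Protocol 14.1.2 requires, with no added draw, visit or procedure. Halts for SMC review become somewhat more likely, because the laboratory bullet has no persistence condition and Appendix C already grades a haemoglobin fall of 2.1 g/dL as Grade 3. Such a halt is a review and does not in itself terminate the trial.

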6.6.1. Sentinel Group Halting Rules

The following halting rules will be applied in the 48 hours following sentinel group vaccination (n = 2 subjects per cohort) for review by the SRC and if any are met, the PI will notify ORA PSSO within 24 hours and further vaccinations will be halted pending SMC review:

- Any SAE regardless of the relationship to the vaccine (with the exception of death or hospitalization that was the result of trauma or accident)
- Type 1 hypersensitivity reaction (anaphylaxis or generalized urticarial)
- Any Grade 3 systemic adverse event (solicited and unsolicited)
- Any Grade 3 local adverse event (solicited and unsolicited) that has not reduced to a Grade 1 or 2 at 48 hours post vaccination⁵

6.6.2. Study Termination Criteria

The PI, research monitor/independent safety monitor (RM/ISM), sponsor's representative, the UMB IRB, DMID, or the FDA may stop or suspend the use of this product at any time.

6.7. Trial Treatment Randomization Codes

A single document delineating the randomized assignment of subjects to vaccine groups will be generated and maintained in a secure location as part of the regulatory file. During the study, investigators, research coordinators, University of Maryland's IDS, representatives of the sponsor and applicable regulatory authorities will have access to this list if required by their duties.

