6.3. Measures Taken to Minimize/Avoid Bias

6.3.1. Randomization

A randomization plan will be used to allocate subjects into experimental groups, per the study priorities described in Section 6.2. In addition, as of Version 5.0, ten replacement subjects will be enrolled into Group 6. A fixed random allocation will ensure that the groups are balanced in size at the end of experiment.

Designated study personnel (excluding the principal investigator [PI] and other investigators) will fill the vaccine cohorts as potential subjects successfully complete the screening process and are deemed eligible to participate by the PI (or another designated investigator). For the purposes of this study, the groups will be defined as follows, and each subject will receive one dose of vaccine on Days 0, 28, and 56.

Group 1 (12 subjects): HTNV by ID EP

Group 2 (12 subjects): HTNV by IM EP

Group 3 (12 subjects): PUUV by ID EP

Group 4 (12 subjects): PUUV by IM EP

Group 5 (12 subjects): HTNV/PUUV by ID EP

Group 6 (22 subjects): HTNV/PUUV by IM EP

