6.3.2. Blinding

Blinding is not applicable and will not be used in this protocol.

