7.2. Eligibility Screening

Each subject must meet all inclusion and no exclusion criteria. Subjects who have signed the informed consent form and successfully completed the assessment of understanding quiz will provide a medical history and undergo a physical examination and clinical safety laboratory tests

administered for screening. The PI or other study physician will make the final decision of the eligibility. Only eligible subjects will be given the investigational product.

Refer to Section 4.8 for a detailed description of the subject population.

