13. Any confirmed or suspected immunosuppressive or immunodeficient condition, including HIV infection or use of anticancer chemotherapy or radiation therapy (cytotoxic) in the 3 years prior to screening.
14. Administration of chronic (defined as more than 14 days) immunosuppressants or other immune-modifying drugs within 6 months of screening. For corticosteroids, this will mean prednisone, or equivalent, greater than or equal to 5 mg/day. Intranasal, inhaled (< 800 beclomethasone mcg/day), and topical steroids are allowed.
15. Has current or past diagnosis of schizophrenia, bipolar disease, or other psychiatric diagnosis that may interfere with subject compliance or safety evaluations.
16. Has been hospitalized for psychiatric illness, history of suicide attempt, or confinement for danger to self or others within 10 years prior to screening.
17. Any chronic or active neurologic disorder, including Guillain-Barré syndrome, seizures and epilepsy, excluding a single febrile seizure as a child.
18. Syncopal episode within 12 months of screening.
19. Suspected or known current alcohol and/or illicit drug abuse within the past 5 years based on self-reporting and physical exam.
20. Any medical, psychiatric, social condition, occupational reason, or other responsibility that, in the judgment of the investigator, is a contraindication to protocol participation or impairs a subject's ability to give informed consent or to comply with the protocol schedule.
21. Pregnant or lactating female, or subject plans to father a child or become pregnant during the study period.

22. Current employee or staff paid entirely or partially by the contract for this trial, or staff who are supervised by the PI or subinvestigators.
23. Subjects with implanted electronic devices stimulation device, such as cardiac demand pacemakers, automatic implantable cardiac defibrillator, nerve stimulators, or deep brain stimulators.
24. Bleeding diathesis or condition associated with prolonged bleeding time, as determined through measurement of PT/PTT (prothrombin time/partial thromboplastin times) during screening labs, that would contraindicate ID or an IM injection.
25. History of cardiac arrhythmia or palpitations or abnormal arrhythmia noted on ECG performed at screening (eg, supraventricular tachycardia, atrial fibrillation, frequent ectopy) prior to study entry. Measurement of sinus bradycardia (ie, < 50 beats per minute on exam) at screening.
26. History of diabetes type 1 or 2

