4.2. Measures Taken to Minimize/Avoid Bias

4.2.1. Randomization

Randomization will take up to four stages, depending on which of four scenarios is determined by sentinel group analysis. Groups 2 and 4 and also 5 and 6 have sentinels as part of the study design because these groups are highest doses offered. Groups 1 and 3 do not have sentinel subjects. If any sentinel testing halts Groups 2, 4, 5 or 6, then Groups 1 and 3 can proceed. It is the study team's preference to test Groups 1 and 3 at the end, assuming Scenario 4 is feasible, so the workflow has been described to enroll as many participants as possible from Groups 5, 6, 1 and 3 at the same time.

Stage 1: Four sentinel subjects are randomly assigned to either Group 2 or 4 with a 1:1 allocation ratio to form the first two sentinel groups (i.e., 2 sentinel subjects per group).

Trial Enrollment Scenario 1 (N=28):

If sentinel halting criteria are met after Stage 1, no additional participants will be assigned to Groups 2 or 4, and no participants will be assigned to Groups 5 or 6. An additional set of 24 participants will be equally randomized into Groups 1 or 3 using a permuted block randomization with a block size of 6. Hence a total of 28 participants (12 in Group 1, 2 in Group 2, 12 in Group 3, and 2 in Group 4) will be enrolled in the trial in this scenario.

Stage 2: If no halting criteria are met for Groups 2 and 4 with $n=2$ sentinels per group, then additional 20 subjects will be enrolled and randomized into Groups 2 and 4 ($n=10$ more participants per group, for a total of $n=12$ per group). At this time there will be 24 participants randomized into Groups 2 and 4.

Trial Enrollment Scenario 2 (N=48):

If study halting criteria are met after Stage 2, no participants will be assigned to Groups 5 or 6. An additional set of 24 participants will be equally randomized into Groups 1 or 3 using a permuted block randomization with a block size of 6. Hence a total of 48 participants (12 in Group 1, 12 in Group 2, 12 in Group 3, and 12 in Group 4) will be enrolled in this scenario.

Stage 3: If no halting criteria are met by the completion of Stages 1 and 2, four sentinel subjects will be randomly assigned to either Group 5 or 6 with a 1:1 allocation ratio to form two additional sentinel groups (i.e., 2 sentinel subjects per group).

Trial Enrollment Scenario 3 (N=52):

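### Protocol 6.7 allows investigators who decide eligibility to see the assignment list before eligibility is final, which does not fit the safeguard in 6.3.1 (minor)

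*Protocol*

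**What the plan says.** Protocol 6.7 describes a single document of random assignments that "will be generated and maintained in a secure location as part of the regulatory file". It names investigators, research coordinators, the investigational pharmacy (IDS), sponsor representatives and regulators as people who, during the study, "will have access to this list if required by their duties". SAP 4.2.1 repeats this and adds that the statistician generates the list in advance, so future assignments are on it before the subjects enter.

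Other sections set the context:

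- **Eligibility (protocol 7.2):** "The PI or other study physician will make the final decision of the eligibility". Some criteria are discretionary. Exclusion 20 in protocol 7.4, for example, covers any condition that "in the judgment of the investigator, is a contraindication to protocol participation".
- **Blinding (protocol 6.3.2):** "Blinding is not applicable and will not be used in this protocol".
- **Filling the groups (protocol 6.3.1):** "Designated study personnel (excluding the principal investigator [PI] and other investigators) will fill the vaccine cohorts", once subjects have passed screening and an investigator has found them eligible.
- **Allocation method (protocol 6.3.1):** "A fixed random allocation will ensure that the groups are balanced in size at the end of experiment". The protocol gives no block size and no release procedure.

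Neither document defines the duties that justify access or the point in a subject's enrolment at which access may begin.

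**The concern.** Section 6.3.1 stands under the heading on avoiding bias, and its purpose is plain: those who judge eligibility should not be those who assign groups. Section 6.7 weakens that separation by naming the same investigators as possible holders of the list, with no bar before eligibility is settled. Coordinators are a second gap. Section 6.3.1 excludes only investigators from cohort filling, so a coordinator could both fill cohorts and hold the list.

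Foreknowledge matters only where there is room to act on it, and here there is some. Exclusion 6 rests on the investigator's assessment of muscle mass, which is relevant to the ID v IM contrast. Exclusion 20 rests on judgment. Out-of-range screening values may be rechecked at the investigator's discretion, and an evolving acute illness delays vaccination. Someone who knows the next assignment could, even unintentionally, let it influence who enters or when. The masked serum labels in protocol 9.2 protect the titer measurement but not the composition of the groups.

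**Working it through.** **1. The passages side by side.** Protocol 6.3.1 bars investigators from filling cohorts. Protocol 7.2 gives them the eligibility decision. Protocol 6.7 and SAP 4.2.1 give them conditional access to a list that already holds future assignments. Nothing orders these steps so that eligibility is recorded before an assignment can be seen.

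**2. How many subjects.** Protocol Appendix B gives 36 enrolled by March 2020, then 2 Group 5 sentinels, 24 for Groups 1 and 3, and 20 for Groups 5 and 6.

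- Check against the stated maximum: 36 + 2 + 24 + 20 = 82, which agrees with the synopsis.
- The two sentinels have only one possible group, so they are not at issue.
- Allocated between two groups under Version 6.0: 24, plus up to 20 if protocol 6.2's 4-month condition is met. That is 24/82 = 29%, rising to at most 44/82 = 54%.

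**3. What sight of the list adds.** With the list, every unreleased assignment is knowable. Without it, staff in an open trial still see past assignments and can guess the group with more places left. For two groups of n with fixed totals, the expected number of correct guesses among 2n is

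E = n + (4^n / C(2n, n) − 1) / 2

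| Set | n | 4^n / C(2n, n) | E | Share correct |
|---|---|---|---|---|
| Groups 1 v 3 | 12 | 16,777,216 / 2,704,156 = 6.204 | 14.60 of 24 | 60.8% |
| Groups 5 v 6 | 10 | 1,048,576 / 184,756 = 5.675 | 12.34 of 20 | 61.7% |
| Both | | | 26.94 of 44 | 61.2% |

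Chance alone gives 22 of 44. The list adds 44 − 22 = 22 assignments over chance. Guessing without it adds 26.94 − 22 = 4.94. Withholding the list therefore removes 17.06 of 22, or 78%, of the excess foreknowledge.

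**4. Which comparisons are exposed.** The pairs in SAP Table 4.3 are 1-2, 3-4, 5-6, 1-5, 3-5, 2-6 and 4-6. Foreknowledge of the list can distort only a choice between groups being filled together.

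- Groups 1 and 3 are filled together, but 1 v 3 is not a planned pair.
- Groups 5 and 6 are filled together, and 5 v 6 is planned. With full enrolment, Version 6.0 randomization supplies 10 of 12 subjects in Group 5 and 10 of up to 22 in Group 6, or 20 of 34.
- The other six pairs compare groups filled at different stages, where timing reveals the group whether or not the list is seen.

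**The case against.** The best defence is that the sections can be read together. The list is kept secure, access depends on duties, and investigators have no cohort-filling duty that would require future assignments. The trial is also expressly not sized to show group differences (protocol 11.2, SAP 5), and the SAP specifies no between-group test of titers. All of this stands, and it is why the point is minor. It does not close the gap: naming investigators and coordinators without defining the duty or the timing leaves early access permitted.

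A reader might infer several stronger things that the documents do not support:

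- **That concealment is defeated.** The text allows conditional access. It does not show that anyone has used it.
- **That the SAP's block size makes the remaining assignments predictable.** The SAP does describe Groups 1 and 3 being allocated "using a permuted block randomization with a block size of 6", but only in its halting Scenarios 1 to 3. Its no-halt scenario uses blocks of 8 across four groups. The SAP dates from January 2019, and protocol 6.2 introduces a new randomization approach with Version 6.0, which states no block size. Predictability figures based on blocks of six cannot be applied to these subjects.
- **That more than half the trial is certainly affected.** The 54% is an upper bound, because the last 20 subjects are conditional.
- **That these are the only groups randomized together.** Groups 2 and 4 were too.

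**Conclusion.** The access rule in protocol 6.7 and SAP 4.2.1 is looser than the safeguard in 6.3.1 intends, and the two should be reconciled. The point concerns 24 subjects and up to 20 more. Among the planned seroconversion comparisons it touches only the ID v IM contrast within the combination vaccine, and only that contrast's Version 6.0 subjects. No breach or resulting bias is shown.

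The 61% figure assumes equal allocation to fixed totals of 12/12 and 10/10, with staff knowing those totals and all past assignments. It shows that withholding the list restores most, but not all, of the concealment. Severity is minor: the effect on conclusions is limited, and the correction is simple.

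**What to change.** In protocol 6.7 and SAP 4.2.1:

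- Limit access to unreleased assignments to the study statistician and the investigational pharmacy (IDS).
- Release each assignment to the designated cohort-filling staff only after that subject's eligibility has been signed by the investigator.
- Allow investigators and coordinators to see assignments already made, which covers their duties in an open-label trial.
- Add a cross-reference to 6.3.1 so that the two sections state one rule.

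The cost is a change of wording, with no added staff. SAP 4.2.1 needs revision anyway, since it still describes the 72-subject staged scheme. The documents do not show whether the remaining assignments have been issued. If they have, what remains is to record in the study report who had access to the list and when.
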